4.12. Safety analyses

Safety data will be summarized for the safety population (SS). Unless otherwise stated, unscheduled visit results will be included in date/time chronological order, within patient listings only.

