- e. Complete Physical Examination should take place at Screening, Day 1 / Baseline and next during the Follow- up period (Day 99), at the end of the study (Day 113) and in case of early withdrawal.
- f. Targeted Physical Examination should be performed on Day 8; 57 and 85.
- g. An ECG is to be performed during the screening period and next on Day 1/ Baseline, Day 8, Day 85, Day 113 and in case of early withdrawal. The ECG procedure may be performed as well at other times, at the discretion of the Investigator if there were findings during a previous examination or in the case of a new/open adverse event (AE).
- h. Chest radiograph (posterior-anterior and lateral views are recommended, however local guidelines should be followed) is required at Screening. A chest X-ray or other appropriate diagnostic imaging modality (ie, CT or MRI) performed within 12 weeks prior to Screening and read by a qualified radiologist with no evidence of current, active TB or previous inactive TB, general infections, heart failure or malignancy may substitute for the chest X-ray taken at Screening. Documentation of the official reading must be located and available in the source documentation.
- i. Laboratory tests may be repeated once during the screening period; the last value will be used to determine eligibility. Single repeats of laboratory tests are consisted of Blood Chemistry, Haematology, Coagulation, C-Reactive Protein (CRP), Erythrocyte Sedimentation Rate (ESR), Anti CCP Antibodies (ACPA) and Urinalysis.
- j. Blood Chemistry, Haematology, Coagulation will be tested at Screening and next on Day 1/Baseline; 8; 29; 57; 85; 99; 113 and in case of early withdrawal.
- k. RF parameter is to be evaluated at Screening, on Day 1/ Baseline; Day 8, 29, 57, 85, during the Follow up visits: Day 99; at the end of the study (Day 113) and in case of early withdrawal.
- l. C- reactive protein (CRP) will be assessed at Screening and on Day 1/Baseline; 8; 29; 57; 85; 99; 113 and in case of early withdrawal. If patient's CRP level is below 7 mg/L on Screening visit, it is possible to perform CRP measurement once again within 28 days of Screening period, provided at least 14 days since initial CRP measurement and prior to Day -5 before Baseline.
- m. ESR will be performed during the screening period and during the treatment period: on Day 1; 8, 29, 57, 85 and during the follow up visits: Day 99; at the end of the study (Day 113) and in case of early withdrawal.

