**Pregnancy Testing**

Serum/urine human beta chorionic gonadotrophin (women of childbearing potential only)

---

Any value outside the normal range will be flagged for the attention of the Investigator or qualified designee at the site. The Investigator or designee will indicate whether the value is of clinical significance. If the result of any test (or repeat test, if done) from the samples taken during the Screening Period is indicated as clinically significant, the subject will not be allowed into the study. Additional testing during the study may be done if medically indicated. If a clinically significant abnormality is found in the samples taken after dosing, during the study, and/or at the Follow-up Visits, it should be recorded as an AE and the subject will be followed until the test(s) has (have) normalized or stabilized, at the discretion of the Investigator.

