2.1.2. Secondary endpoints

Clinical Efficacy:

- Proportion of subjects with DAS28-CRP remission at Weeks 4; 8; 12 and 16.
- American College of Rheumatology (ACR)20, ACR 50, ACR 70, and ACR 90 responder rates (Weeks 4, 8 and 12).
- Change from Baseline in the Tender/Painful and Swollen Joint Count (Weeks 4, 8 and 12).
- Change from Baseline in the Physician's Global Assessment (PhGA) of Arthritis (Weeks 4, 8 and 12).

Patient Reported Outcome:

- Change from baseline in the Patient's Assessment of Arthritis Pain (PAAP) VAS and Patient Global Assessment of Arthritis (PtGA, VAS) at Week 4, 8, and 12.
- Change from baseline in the Health Assessment Questionnaire – Disability Index (HAQ-DI) at Week 4, 8, and 12.
- Change from baseline in the SF-36 RAND 8 Domain scores and Physical Component Score (PCS) and Mental component score (MCS) at Week 12.
- Change from baseline in the Functional Assessment of Chronic Illness Therapy Fatigue (FACIT-F) total score at Week 12.

Safety:

Safety and tolerability of CPL409116: vital signs (blood pressure (BP), pulse and temperature), laboratory tests, Adverse Events (AEs) and Serious Adverse Events (SAEs), 12-lead electrocardiogram (ECG):

- Incidence and severity of adverse events, serious adverse events, and withdrawals due to adverse events (Baseline through Week 16).
- Incidence of abnormality in clinical chemistry parameters (Baseline through Week 16).
- Incidence of abnormality in haematological parameters (Baseline through Week 16).
- Change from baseline in blood pressure measurement (Baseline through Week 16).
- Change from baseline in pulse rate measurement (Baseline through Week 16).
- Change from baseline in temperature measurement (Baseline through Week 16).
- Incidences of targeted medical adverse events (Baseline through Week 16).

Pharmacokinetics:

- CPL409116 and metabolite M3 pharmacokinetic variables: $AUC_{(0-6h)}$, C_{max} , T_{max} , $T_{1/2}$ (if possible) and K_{el} (if possible) determined on Day 1, 8, 57 and 85.
- CPL409116 pharmacokinetic variables: C_{0h} , $C_{2.5h}$ determined on Day 29.

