4.4. Specifications for plots

Unless otherwise specified, plots for continuous variables will present mean and SD for each randomized treatment group. LS means calculated from MMRM models will be presented as bars with whiskers representing 95% confidence intervals (CI). Binary endpoints will be presented as forest plots – with a point representing proportion of subjects meeting the endpoint and whiskers representing a 95% CI. Results from logistic regression will also take form of a forest plot – point with whiskers, where point represents odds ratio and whiskers confidence interval.

Time to remission will be presented graphically using Kaplan-Meier curve – a series of declining horizontal steps.

For safety analysis distribution of data will be presented as line and point and whisker plots (presenting mean and standard deviations) or boxplots (for variables with highly skewed distributions – such as CRP). For boxplot top and bottom of the box will represent lower and upper quartile respectively. Thick line in the middle of the box will be median. Whiskers will represent the lowest value at most $Q1+1,5*IQR$ (inter quantile range) and the largest value no further than $Q3+1,5*IQR$. Points will represent potential outliers. Treatment groups will be presented as separate panels within a figure.

Data will be shown for each randomized treatment group. Data collected during unscheduled visit will not be shown on plots unless otherwise specified.

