4.12.2. Safety laboratory data

Laboratory data will be summarized by type of laboratory test after all results are converted to standard SI units (according to algorithms presented in Data Validation Plan). Descriptive statistics will be calculated for each laboratory parameter at baseline (Day 1) and at each scheduled time point. Shift tables using the categories 'lower than normal range', 'within normal range' and 'higher than normal range' will be provided for each numeric parameter, comparing the baseline value to all post-baseline values. For results expressed as category (in urinalysis) shift tables will present categories: normal and abnormal. Moreover, change from baseline values will also be presented.

Other urinalysis parameters, than those pre-specified in the eCRF, will be listed only.

Listings of each laboratory parameter will be provided, marking changes from norm. A separate listings will be produced for clinically significant abnormal results (for purpose of presentation in the statistical report/CSR).

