4.12.4. Electrocardiograms

ECG variables that will be analyzed including: QTc and QRS intervals as well as ECG findings.

ECG summaries will take form of tables for raw data and changes from baseline (values collected during Day 1) as well as percentage of abnormal values for ECG findings. In addition, shift tables presenting number of patients that either developed abnormalities since baseline will be provided.

The number of patients with at least one clinically relevant finding detected during the ECG examination will be summarized in frequency tables for each scheduled assessment or visit.

Change from baseline values of ECG parameters will take form of boxplots for each study arms.

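### SAP 4.12 keeps unscheduled laboratory results out of the tables, and no per-patient, whole-period count is defined for the chemistry and haematology incidence-of-abnormality endpoints

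*SAP*

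**What the plan says.** **Default.** SAP 4.12 states: "Unless otherwise stated, unscheduled visit results will be included in date/time chronological order, within patient listings only". SAP 4.4 adds: "Data collected during unscheduled visit will not be shown on plots unless otherwise specified".

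**Endpoints.** SAP 2.1.2 (Secondary endpoints) lists "Incidence of abnormality in clinical chemistry parameters (Baseline through Week 16", and a matching endpoint for haematology. Blood pressure, pulse and temperature are change-from-baseline endpoints. ECG has no incidence endpoint of its own.

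**Tables.**
- Laboratory (SAP 4.12.2): "Descriptive statistics will be calculated for each laboratory parameter at baseline (Day 1) and at each scheduled time point". The next sentence defines low/normal/high shift tables "comparing the baseline value to all post-baseline values".
- Vital signs (SAP 4.12.3): percentage abnormal, and shift tables described in the same way.
- ECG (SAP 4.12.4): patients with a clinically relevant finding "will be summarized in frequency tables for each scheduled assessment or visit".

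**Source of unscheduled results.** Protocol 1.3 allows unplanned visits to protect the patient. On laboratory tests, Protocol 8.2 says: "Additional testing during the study may be done if medically indicated". On ECGs, footnote g to Table 1 says: "The ECG procedure may be performed as well at other times, at the discretion of the Investigator if there were findings during a previous examination", and it also allows them for a new or open adverse event. Footnote d gives the same triggers for vital signs.

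**Clinical significance.** Protocol 8.2 requires a clinically significant laboratory abnormality found after dosing to be recorded as an adverse event.

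**The concern.** Incidence from Baseline through Week 16 is a whole-period quantity: did this patient have an abnormal value at any time? The SAP never defines that count. It can define one elsewhere, since DAS28-CRP remission in 4.11.2 is presented at any time as well as by visit. For laboratory safety it offers scheduled-visit statistics and a shift table whose scope is unclear, under a default that sends unscheduled results to listings.

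Those results come from tests done for a reason. Leaving them out of a whole-period incidence can only lower it or leave it unchanged. Two programmers could also read the shift-table phrase differently and report different counts from the same database.

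**Working it through.** The plan states no figure on this point, so there is none to reproduce. The check sets the passages side by side and then counts days.

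**1. Where a post-dose chemistry or haematology value ends up**

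| Value | Where the SAP puts it |
|---|---|
| Out of range at a scheduled visit | Descriptive statistics, shift table, listing |
| Out of range on an unscheduled test, clinically significant | Adverse event tables, listing of significant results |
| Out of range on an unscheduled test only, not clinically significant | Patient listing; shift table only if the phrase overrides the default |
| Unscheduled and more extreme than a scheduled abnormal value in the same direction | Patient already counted; the extreme is outside the scheduled-visit minimum and maximum |

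The third row affects the endpoint count. The fourth affects only whether the worst value reaches a table.

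**2. Gaps between scheduled assessments** (Table 1 footnotes d, g and j)
- Laboratory and vital signs, Days 1, 8, 29, 57, 85, 99, 113: gaps of 7, 21, 28, 28, 14 and 14 days.
- ECG, Days 1, 8, 85, 113: gaps of 7, 77 and 28 days.

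**3. Illustration of what scheduled days alone can see.** Two assumptions are not in the documents: onset is uniform over Days 1 to 113 (112 days), and an abnormality lasts d days. It is seen if onset falls within the d days up to and including a scheduled post-baseline day, so

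share seen = (length of the union of the intervals [t − d, t], cut off at Day 1) / 112.

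For d = 7, the laboratory days give 6 × 7 = 42 and 42/112 = 37.5%. The ECG days give 3 × 7 = 21 and 21/112 = 18.8%. For d = 14, the laboratory intervals cover 7 + 5 × 14 = 77 days (Day 8 is cut off at Day 1), so 77/112 = 68.8%. The ECG intervals cover 7 + 14 + 14 = 35 days, so 35/112 = 31.3%.

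| Assumed duration (days) | Seen on a laboratory/vital sign day | Seen on an ECG day |
|---|---|---|
| 3 | 16% | 8% |
| 7 | 38% | 19% |
| 14 | 69% | 31% |
| 21 | 88% | 44% |

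This shows that short abnormalities can fall between visits. It does not show how many an extra test would find, because the documents give no frequency of unscheduled testing.

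**4. Unit of size.** With 25 patients per arm, one uncounted patient is 100/25 = 4 percentage points of that arm's incidence. This holds for any binary outcome at this sample size and does not estimate the effect of the rule.

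**The case against.** The strongest reply has four parts.

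- **Shift tables.** The default yields where the SAP states otherwise. SAP 4.12.2 moves from scheduled time points in one sentence to "comparing the baseline value to all post-baseline values" in the next, which can fairly be read as including unscheduled results. This stands as a possible reading. The phrase names neither unscheduled results nor the default, so the scope remains open.
- **Significant abnormalities are counted.** A clinically significant neutropenia or ALT rise on an extra test becomes an adverse event. The adverse event tables are not tied to visits and give patient counts by term and maximum severity. This stands and narrows the loss to values not judged clinically significant. It does not remove it, because the endpoint is abnormality, whether or not clinically significant.
- **Retests may add nothing.** Some follow an abnormal result at a scheduled visit that is already counted, and others document a return to normal. This also stands.
- **Unequal testing.** Patients tested more often have more chances to show an abnormality, which is a reason for scheduled-only summaries. It argues for showing both counts.

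A reader might also infer that early-withdrawal results are lost in the same way. The documents do not support that: Early Withdrawal has its own column in Table 1 and its own laboratory panel in Protocol 9.4, and footnote j lists it with the scheduled laboratory days. The SAP does not, however, say under which time point its results are tabulated.

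**Conclusion.** The gap is real but narrow. Chemistry and haematology incidence through Week 16 has no per-patient definition. Under the listings-only default, an out-of-range value seen only on an unscheduled test, and not recorded as an adverse event, is left out. Incidence can then be understated. This rests on the default governing the shift tables; if their wording overrides it, the problem reduces to an undefined endpoint count and an unclear sentence.

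Three stronger readings are not supported:
- **Vital sign and ECG values drop out of incidence endpoints.** There are none for these measures. The rule affects only their percentage-abnormal, shift and frequency tables.
- **The arm with most retesting is biased most.** The documents give no testing frequencies by arm and do not show that retests bring in new abnormalities, so neither the direction nor the size of a between-arm bias is established.
- **The low/normal/high categories must be replaced by threshold counts based on the exclusion-criterion limits.** Those are screening limits. Such a table is optional and not needed to close this gap.

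These are descriptive secondary safety endpoints, and the efficacy analysis is untouched. The change is still worth making because it is cheap and settles what the endpoint means.

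**What to change.** - **SAP 4.12.2:** define chemistry and haematology incidence per patient as any abnormal value after first dose through Week 16, using scheduled, unscheduled and early-withdrawal results. Base the laboratory shift tables on the worst post-baseline value in each direction, and say that this overrides the 4.12 default. Giving the minimum and maximum of those worst values would also put the extremes in a table.
- **SAP 4.12.3 and 4.12.4:** state that the shift tables include unscheduled and early-withdrawal values. Add a count of patients with any post-baseline abnormal value (vital signs) or clinically relevant finding (ECG) on the same basis.
- **By-visit descriptive statistics and plots:** keep these on scheduled visits only.
- **Scheduled-only incidence:** show it next to the all-results count, so that the effect of unequal testing is visible.

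The cost is some SAP wording and a few extra tables from data already collected. No visit, test or treatment rule changes.

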4.12.1. Adverse events analysis

Any undesirable signs, symptoms or medical conditions occurring or worsening of pre-existing conditions between signing informed consent and the first administration study medication are considered as pre-treatment AEs. Undesirable signs, symptoms or medical conditions or worsening of pre-existing conditions occurring after the first administration of study medication are considered as treatment emergent adverse events (TEAEs).

A TEAE will be analyzed as related to study medication (i.e. as adverse drug reaction, ADR) if the relationship to study treatment was documented as 'unlikely', 'possible', 'probable', or 'definite' or if the relationship to study treatment is missing.

An overview table presenting the incidence of the following AE categories will be presented. Percentage of patients in each category will be compared between treatments as a difference in proportions between treatments including a 95% CI based on the Agresti – Caffo method (2000):

- All AEs
- Pre-treatment AEs
- Serious AEs (SAEs) (including pre-treatment SAEs)
- Treatment emergent AEs (TEAEs)
- Treatment emergent SAEs (TESAEs)
- Severe TEAEs
- Related TEAEs
- Related severe TEAEs
- TEAEs leading to reduction of dose
- TEAEs leading to interruption of dose
- TEAEs leading to permanent discontinuation (i.e. withdrawal) of study medication
- Related TEAEs leading to permanent discontinuation of study medication
- AEs leading to death (i.e. outcome of AE is fatal)
- TEAEs leading to death
- Related TEAEs leading to death
- Targeted medical adverse events

Targeted medical adverse events are defined in section 4.2.14.

All treatment emergent AEs (TEAEs) and all serious TEAEs will be tabulated by MedDRA System Organ Class (SOC) and preferred term (PT) presenting the number and percentage of patients reporting the AE and the number of AEs reported. Additional tables will distinguish the events by whether the AE was related to study medication and by maximum severity.

All AEs documented in the eCRF will be listed by patient. Data listings will include patient ID, treatment group, verbatim term, preferred term, system organ class, start and stop date and relative day of the AE, severity, medications (yes/no), seriousness, action taken with study medication, relationship to study medication, and outcome will be provided. TEAEs will be

flagged as such. In addition, separate listings for all SAE's, deaths and AEs leading to discontinuation (action taken with study treatment = drug withdrawn or AE is reason for early termination) will be presented.

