#### **Causality**

The Investigator will assess the causality/relationship between the study drug and the AE. One of the categories described in Table 5 should be selected based on medical judgment, considering the definitions below and all contributing factors.

Table 5. Assessment of Relationship of Adverse Events to Investigational Product.

Related	A clinical event, including laboratory test abnormality, occurs in a plausible time relationship to treatment administration, and which concurrent disease or other drugs or chemicals cannot explain. The response to withdrawal of the treatment (dechallenge*) should be clinically plausible. The event must be definitive pharmacologically or phenomenologically, using a satisfactory rechallenge† procedure if necessary.
Probably related	A clinical event, including laboratory test abnormality, with a reasonable time sequence to administration of the treatment, unlikely to be attributed to concurrent disease or other drugs or chemicals, and which follows a clinically reasonable response on withdrawal (dechallenge). Rechallenge information is not required to fulfill this definition.
Possibly related	A clinical event, including laboratory test abnormality, with a reasonable time sequence to administration of the treatment, but which could also be explained by concurrent disease or other drugs or chemicals. Information on treatment withdrawal may be lacking or unclear.
Unlikely to be related	A clinical event, including laboratory test abnormality, with a temporal relationship to treatment administration which makes a causal relationship improbable, and in which other drugs, chemicals or underlying disease provide plausible explanations.
Unrelated	A clinical event, including laboratory test abnormality, with little or no temporal relationship with treatment administration. May have negative dechallenge and rechallenge information. Typically explained by extraneous factors (e.g., concomitant disease, environmental factors or other drugs or chemicals).

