##### **Adverse events**

All AEs will be listed. The number and percent of subjects experiencing an event will be tabulated for each SOC and preferred term. The AEs will also be tabulated according to intensity and causality.

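### SAP 4.12.1 counts adverse events graded unlikely as drug-related, which inflates the related-event tables in every arm, and its causality labels do not match protocol Table 5

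*SAP*

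**What the plan says.** Protocol 8.1 (Causality) has the investigator grade every adverse event: "One of the categories described in Table 5 should be selected based on medical judgment". Table 5 has five grades: *Related*, *Probably related*, *Possibly related*, *Unlikely to be related* and *Unrelated*. The fourth is for events whose timing "makes a causal relationship improbable, and in which other drugs, chemicals or underlying disease provide plausible explanations". For the first, the table says "The event must be definitive pharmacologically or phenomenologically".

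Protocol 10.7 says of the analysis: "The AEs will also be tabulated according to intensity and causality". It does not say which grades form a related group.

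SAP 4.12.1 supplies that cut. Its rule begins "A TEAE will be analyzed as related to study medication (i.e. as adverse drug reaction, ADR" and applies when the relationship was "documented as 'unlikely', 'possible', 'probable', or 'definite", and also when it is missing. Four rows of the overview table then use the related group: related events, related severe events, related events leading to permanent discontinuation, and related events leading to death. Arms are compared by differences in proportions with 95% Agresti-Caffo intervals. Further tables split events into related and not related. The listings show the recorded relationship for each event.

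**The concern.** The SAP equates its related group with adverse drug reactions, yet the group includes events for which the investigator found a causal link improbable and another explanation plausible. That reverses the recorded judgement. Only *Unrelated* is left out, and Table 5 reserves that grade for events with little or no temporal link to treatment.

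The design makes the fourth grade likely to be used. Every patient has active rheumatoid arthritis and takes methotrexate, and inclusion criterion 6 itself mentions nausea or vomiting and hepatic or haematologic toxicity from that drug. An event during dosing that the investigator puts down to methotrexate or to the disease can fit *Unlikely to be related*, on placebo as much as on CPL409116. The SAP would report it as a reaction to study medication.

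The second problem is wording. *Definite* is not a protocol grade, and the protocol's highest grade, *Related*, is not named in the SAP rule. A programmer has to guess the mapping.

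**Working it through.** The plan states no figure on this point, so the main check sets the two scales side by side.

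| Protocol Table 5 grade | Nearest SAP 4.12.1 label by rank | Counted as related? |
|---|---|---|
| Related | definite | yes, if mapped by rank |
| Probably related | probable | yes |
| Possibly related | possible | yes |
| Unlikely to be related | unlikely | yes |
| Unrelated | none | no |
| Missing | missing | yes |

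**Lower end.** Four of the five grades, plus missing, count as related. *Unlikely* is named explicitly, so its inclusion does not depend on interpretation.

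**Upper end.** None of the four SAP labels is verbatim Table 5 wording, so the list reads as a paraphrase of the scale. By rank, *definite* stands for *Related*, and Table 5 requires a *Related* event to be definitive. Under strict label matching *Related* would find no match, but the full Table 5 labels of the other three grades would fail too. The eCRF values are not in the documents.

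**Size.** No event counts by grade are given, so the following is illustrative only.

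Inputs: 25 patients per arm (SAP 2.2). Assumed: possibly, probably or definitely attributed events in 10% of placebo and 30% of top-dose patients, and *unlikely* events in 30% of each arm. Counts are expected values.

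The Agresti-Caffo method uses p̃ = (x + 1)/(n + 2), with half-width 1.96 × √{[p̃₁(1 − p̃₁) + p̃₂(1 − p̃₂)]/(n + 2)} for equal arms.

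1. Without *unlikely* (10% v 30%, difference 20 points): p̃ = 3.5/27 = 0.130 and 8.5/27 = 0.315. Half-width = 1.96 × √[(0.113 + 0.216)/27] = 0.216, about 22 points. The interval runs from about −3 to +40.
2. With *unlikely*, no patient having both kinds of event (40% v 60%, difference still 20 points): p̃ = 11/27 = 0.407 and 16/27 = 0.593. Half-width = 1.96 × √[(0.241 + 0.241)/27] = 0.262, about 26 points. The interval runs from about −8 to +45.
3. With *unlikely*, the two kinds independent: 1 − 0.9 × 0.7 = 37% and 1 − 0.7 × 0.7 = 51%, difference 14 points. p̃ = 10.25/27 = 0.380 and 13.75/27 = 0.509. Half-width = 1.96 × √[(0.236 + 0.250)/27] = 0.263, about 26 points. The interval runs from about −13 to +39.

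So the planned comparison loses precision, and the difference itself shrinks only if the same patients have both kinds of event. With no *unlikely* events at all, nothing changes.

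**The case against.** The best defence is that the rule is explicit, pre-specified and deliberately inclusive. The same sentence counts missing causality as related, so the SAP errs towards over-reporting and hides nothing. The protocol sets no cut between related and not related, so the SAP breaks no stated split. The listings carry the recorded grade, so a reader can reclassify. All of this is correct, and it limits how serious the point is. It does not remove it. The SAP gives no reason for including *unlikely*, and calling the result adverse drug reactions conflicts with the meaning Table 5 gives that grade. Listings also do not replace the tabulation by causality that protocol 10.7 describes.

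A reader might go further and infer two things that the documents do not support.

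- **That the tables are wrong at both ends of the scale, with the strongest grade dropped.** This would need literal label matching. The SAP labels are paraphrases, *definite* fits the rank of *Related*, and the eCRF values are not available.
- **That the rule obscures the dose signal required by the safety objective.** The safety endpoints in the protocol synopsis and SAP 2.1.2 do not depend on relatedness. Targeted medical events are defined in SAP 4.2.14 by MedDRA terms and seriousness. All treatment-emergent and all serious treatment-emergent events are tabulated regardless of cause. In a double-blind, placebo-controlled trial those comparisons carry the dose signal.

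**Conclusion.** The point stands for the lower end of the scale. As written, SAP 4.12.1 reports events that the protocol calls causally improbable as adverse drug reactions. Wherever such events occur, this raises the four related rows and the related/not-related tables, placebo included, and makes those comparisons less precise. The 22-to-26-point widening of the half-width rests on assumed event rates and the planned 25 per arm; the true size depends on how often the grade is used, which the documents do not say. Both intervals in that illustration include zero, so it shows a loss of clarity and not a reversed conclusion.

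The label mismatch is a mapping risk to close before programming, not an established error. No efficacy result, listed safety endpoint or all-causality table is affected. The correction is worth making because it is small and because related-event counts are easily read as drug effects.

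**What to change.** In SAP 4.12.1:

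1. Check the causality values stored in the eCRF and state how each maps to Table 5.
2. Define a related event, in the exact Table 5 labels, as *Related*, *Probably related*, *Possibly related* or missing. Treat *Unlikely to be related* and *Unrelated* as not related.
3. Replace *definite* with *Related* once the eCRF values are confirmed. Deleting it without that check could create a new mismatch.
4. Add the tabulation by causality grade described in protocol 10.7, so that the effect of the cut is visible.
5. If the inclusive count is wanted, keep it as a labelled sensitivity table and give the reason.

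The definition takes one sentence in the SAP, plus one added table, and needs no new data. The downside is that fewer events are labelled related; the all-event tables stay as planned.
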